1 PROTOCOL SUMMARY

1.1 SYNOPSIS

Title: TRANScranial direct current stimulation for PPost-stroke motor Recovery- a phase II sTudy (TRANSPORT2)

Study Description: TRANSPORT2 is a phase II multi-center transcranial direct current stimulation (tDCS) dosing selection study based on the preliminary efficacy, safety, tolerability and feasibility.

Objectives: **Primary Objective:** To determine whether there is an overall treatment effect among 3 dosing groups (sham+mCIMT, 2 mA+mCIMT, and 4 mA+mCIMT) on day 15 (\pm 2 days) after the start of the intervention in the Fugl-Meyer Upper-Extremity (FM-UE) scale, a measure of motor impairment. Additional outcome measures include the Wolf-Motor-Function-Test (WMFT), a measure of functional motor activity, and the Stroke-Impact-Scale (SIS), a measure of quality of life. Sustained benefit will be assessed at day 45 (\pm 5 days) and day 105 (\pm 10 days).

Secondary Objectives: To confirm that the proposed intervention is safe (no significant differences in rate of adverse events), tolerable (no significant differences in discomfort as measured by Visual-Analog-Scale), and feasible to administer in a multi-site trial (>80% of subjects complete the treatment protocol and no unexplained/unresolved variability by site).

Exploratory Objectives: To examine whether wCST-LL (structural assessment of integrity of descending motor tract) or MEPs (functional assessment of integrity of descending motor tract) or combination of both are correlated with changes in FM-UE scale, and evaluate the utility of these measures as biomarkers for patient selection criteria in the future confirmatory Phase III study. We also

aim to examine whether structural and functional changes within descending motor tracts correlate with changes in motor impairment and functional motor activity.

Endpoints:

Primary Endpoint: Fugl-Meyer Upper-Extremity (FM-UE) scale a measure of motor impairment;

Secondary Endpoints: Wolf Motor Function Test (WMFT) time score, a measure of functional motor activity; Stroke-Impact-Scale hand subscale as an assessment of patient-centered quality of life.

Study Population:

Subject who is 18-80 years of age of any gender or ethnicity, who had first-ever unihemispheric ischemic stroke in past 30-180 days resulting in unilateral limb weakness with FM-UE ≤ 54 (out of 66) that is stable across two baseline visits at the time of randomization and an mRS ≤ 2 pre-stroke. We are planning to enroll 129 subjects across three arms.

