3 OBJECTIVES AND ENDPOINTS

OBJECTIVES	ENDPOINTS	JUSTIFICATION FOR ENDPOINTS
------------	-----------	-----------------------------

Primary		
To determine whether there is an initial overall treatment effect among 3 dosing groups: • sham + mCIMT • 2 mA + mCIMT • 4 mA + mCIMT	FM-UE scale	FM-UE scale is the primary outcome and a measure of motor impairment
Efficacy is measured at day 15 after the initiation of the intervention.	WMFT time score	WMFT is a secondary outcome and a measure of functional motor activity
	SIS Hand Subscale	SIS Hand subscale is a secondary outcome and a measure of the quality of life
Secondary		
To confirm that the proposed intervention is safe, tolerable, and feasible to administer in a multi-site trial setting	Rate of adverse events	Safety needs to be monitored in a phase II study
	Visual Analog Scale	Visual Analog Scale measures tolerability
	Treatment completion rate	80% of treatment completion rate across sites without unexplained/unresolved variability is a measure of feasibility.
Tertiary/Exploratory		
To examine whether wCST-LL (structural assessment of integrity of descending motor tract) or MEPs (functional assessment of integrity of descending motor tract) or combination of both are correlated	wCST-LL (structural)	wCST-LL is a structural measure of integrity of descending motor tract using brain MRI that has shown promise in predicting motor outcomes.

with changes in FM-UE scale, and evaluate the utility of these measures as biomarkers for subject selection criteria in the future confirmatory Phase III study
	
MEPs (functional)
	
MEPs is a functional measure integrity of descending motor tract using TMS that has shown promise in predicting motor outcomes, but two of them have not been collected and compared in the same study.

To examine whether functional or structural changes in motor tracts correlate with changes in impairment and functional motor activity induced by the intervention.
	
Motor Evoked Potentials (MEPs) and Diffusion tensor imaging MRI.
	
MEPs can change in response to rehabilitation; Functional and structural aspects of motor tracts and the interaction between motor regions change after intervention. This change can be captured by comparing TMS and MRI measures before and after treatment

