8.2 ADVERSE EVENTS AND SERIOUS ADVERSE EVENTS

A tDCS questionnaire will be used in each intervention session to assess the common adverse events or tolerability issues associated with its use. Adverse events, including serious adverse events will be collected during the intervention period. Only serious adverse events or clinically related (possibly or definitely) adverse events will be collected after intervention period. Please refer to AE reporting section for details.

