9.4.4 SAFETY ANALYSES

Safety: Analysis Method

IMSM and Data and Safety Monitoring Board (DSMB) will receive periodic safety reports of all reportable adverse events including serious adverse events (SAEs) if there are any. All clinical safety endpoints and SAEs will be summarized by AE code (as provided on the AE CRF) regarding the frequency of the event, the number of subjects having the event, severity, and relatedness to the study treatment. Clinically important adverse events include:

- Severe headache
- Second-degree skin burn
- Clinical seizure
- Neurological deterioration (\geq 4-point increase in NIHSS)

The proportion of subjects experiencing each of these events will be provided in the closed report by intervention arm with two-sided 95% CIs and unadjusted relative risks. Based on the Phase I dose-escalation study, no subjects experienced any of the clinically important adverse events. Fisher's exact tests will be used to assess intervention group differences in the rates of clinically important adverse events.

Tolerability: Analysis Method

Tolerability will primarily be measured through the use of the Visual-Analog scale (VAS), a 10-point scale ranging from 0 (No Discomfort) to 10 (Extreme Discomfort). For the primary analysis, any subject who requests to be withdrawn from the study due to procedure related issues will be imputed as a 10 on the Visual-Analog Scale. Differences in tolerability will be assessed using a Kruskal-Wallis test at a 10% type-I error rate.

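### The safety endpoint is the rate of adverse events, but the protocol's only formal between-arm safety comparison covers a short list of rare events

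*Combined protocol and SAP*

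**What the plan says.** The Synopsis (1.1) sets the secondary objective of confirming that the intervention is "safe (no significant differences in rate of adverse events"), and the table in section 3 names the endpoint as "Rate of adverse events". Neither restricts it to a subset of events.

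Section 8.2 sets what is recorded: "Adverse events, including serious adverse events will be collected during the intervention period". After that the net narrows: "Only serious adverse events or clinically related (possibly or definitely) adverse events will be collected after intervention period".

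Section 9.4.4 gives the analysis in two tiers:

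- General tier: "All clinical safety endpoints and SAEs will be summarized by AE code (as provided on the AE CRF"), covering frequency, number of subjects, severity and relatedness. No arm contrast, test or significance level is attached.
- Formal tier: "Clinically important adverse events include" severe headache, second-degree skin burn, clinical seizure and neurological deterioration (NIHSS up by at least 4). These get proportions by arm with 95% confidence intervals, unadjusted relative risks, and Fisher's "exact tests will be used to assess intervention group differences in the rates of clinically important adverse events".

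The same section reports that in Phase I "no subjects experienced any of the clinically important adverse events". Tolerability is handled separately there, with a Kruskal-Wallis test on the discomfort VAS at the 10% level.

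**The concern.** The criterion in the objective is a comparison between dose groups of one quantity, and the formal analysis compares another. Followed as written, the trial would report Fisher tests on events expected to be close to absent, find no significant difference, and appear to have met a criterion about adverse events in general.

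This matters because the study selects a dose partly on safety, and section 9.4.1 asks whether 4 mA keeps a safety and tolerability profile similar to that of 2 mA. The effects that section 2.3.1 lists as commonly reported (redness, itching, tingling, burning, transient headache) are the likeliest to rise with current. As adverse events, they have no specified contrast.

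The mismatch is separate from the question of how a non-significant safety test should be read. It would remain under any decision rule.

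**Working it through.** **Inputs.** 129 subjects are randomised 1:1:1 (4.1), so 43 per arm. That figure reproduces from 9.2: 31/(1 − 0.08)² = 36.6; 36.6 × 1.15 = 42.1, rounded up to 43. The protocol gives no sample size, power or significance level for any adverse event comparison, so there is no safety figure to reproduce. It also does not say whether the Fisher tests are per event or composite, or three-group or pairwise. I took them per event and tried both groupings.

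**What it takes to reach significance on a rare event (43 per arm).**

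- Pairwise, k events against 0: two-sided p = 2 × C(43,k)/C(86,k). k = 5 gives 0.055; k = 6 gives 0.026. So 6 v 0 is needed at the 5% level, and 5 v 0 at the 10% level.
- Three groups, k events in one arm and none in the other two: p = 3 × C(43,k)/C(129,k). k = 3 gives 0.106; k = 4 gives 0.034. So 4 events are needed at either level.

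**Power for a rare event.** With a true rate of zero elsewhere, power is the binomial chance that the one affected arm reaches the required count.

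| True rates (assumed) | Test | Power at 5% | Power at 10% |
|---|---|---|---|
| 0% v 5% | pairwise | P(Y ≥ 6) = 2% | P(Y ≥ 5) = 6% |
| 0 / 0 / 2% | three-group | 1% | 1% |
| 0 / 0 / 5% | three-group | P(Y ≥ 4) = 17% | 17% |
| 0 / 0 / 10% | three-group | 64% | 64% |

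If no event is seen in an arm of 43, the two-sided 95% upper limit for its rate is 1 − 0.025^(1/43) = 8.2%.

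**Power for the stated endpoint, as subjects with at least one adverse event.** The documents give no overall rate, so these rates are assumptions. Exact power sums Bin(x; 43, p₁) × Bin(y; 43, p₂) over all outcomes for which Fisher's two-sided p is at or below the level.

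| Sham v active (assumed) | Power at 5% | Power at 10% |
|---|---|---|
| 20% v 50% | 80% | 87% |
| 30% v 60% | 74% | 84% |
| 20% v 40% | 45% | 57% |
| 30% v 50% | 40% | 52% |
| 30% v 40% | 12% | 19% |

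If the two comparisons against sham were each run at 2.5%, the first two rows would fall to 70% and 63%.

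**Precision of a risk difference.** The approximate 95% half-width is 1.96 × √[(p₁(1 − p₁) + p₂(1 − p₂))/43]. For 30% v 50% this is 1.96 × √(0.46/43) = 0.203, about 20 percentage points either side.

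**The case against.** A reader might infer that adverse events are never compared between dose groups. The documents do not support that. Section 8.2.4 gives the DSMB a semi-annual closed report of safety data by partially blinded arm, including the most frequent and most serious events, and section 9.4.7 says summaries are presented by dose group. Descriptive by-arm figures are therefore planned. What neither section supplies is a definition of the adverse event rate, an estimate of the difference, or a test, and the closed report is interim monitoring with restricted access.

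A reader might also infer that no between-arm test could show a gradient in discomfort. The Kruskal-Wallis test of the VAS could. But it uses a single score taken at the final treatment session (1.3, footnote 4), with procedure-related withdrawals set to 10. It is a tolerability endpoint and not an adverse event rate.

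Three further points stand in part:

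- Section 9.4 refers details to a statistical analysis plan whose text was not available here, so a comparison of the overall rate may be specified there. Even so, the protocol's own safety section should answer its own endpoint.
- The list of clinically important events is worded as open, although only four are named. Their rarity rests on one Phase I study whose size the protocol does not give.
- Formal tests on pre-specified important events, with description of the rest, is a defensible Phase II design. Rewording the objective to those events would also cure the mismatch, but would leave the common effects without a planned contrast.

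Finally, it would be too strong to say that the trial can reliably test the overall rate. It can do so only for differences near 30 points. Soreness or fatigue from mCIMT, possible in every arm, could dilute an any-event comparison further.

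**Conclusion.** The point holds in this form: the safety objective and endpoint are the rate of adverse events, and the protocol text specifies no formal between-arm comparison of that rate. Its formal comparison covers clinically important events, listed as four, for which non-significance is close to assured if true rates are a few percent: 2% pairwise power for 0% v 5% at the 5% level, and 17% on the three-group test for 0/0/5%. At a true 10% in one arm only, the three-group test would have 64% power, so the conclusion depends on the events being rare, as Phase I suggests. Non-significance on these events cannot carry a statement about adverse event rates overall.

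The assumptions are 43 evaluable subjects per arm, a test per event, the event rates shown, and no contrary provision in the statistical analysis plan. The change should be made because a stated objective lacks its analysis; the primary efficacy result is unaffected.

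**What to change.** In section 9.4.4, add a by-arm analysis for the intervention period, during which all adverse events are collected:

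- the proportion of subjects with at least one adverse event;
- the proportion with at least one adverse event graded Reasonable Possibility or Definitely under 8.2.3.2;
- for each, the risk difference with a 95% confidence interval for 2 mA against sham and for 4 mA against sham.

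Keep the four clinically important events as a further table, and state whether their Fisher tests are per event or composite, three-group or pairwise, and at what level. Base the safety statement on the estimates and intervals, and reword the objective in 1.1 and the entry in section 3 so that they describe this analysis instead of an absence of significant differences. If the statistical analysis plan already contains such a comparison, cross-refer to it and align the wording.

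The cost is text and one more table from data already collected with relatedness. The downside is that intervals of about 20 points either side will be wide for modest differences, and the report should say so.

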1.3 SCHEDULE OF ACTIVITIES (SOA)

Event	Baseline 1	Baseline 2 ³ –	Treatment Sessions (1-10)	Follow Up 1	Follow Up 2	Follow Up 3	End of Study
	Day -20 to -7	Day -6 to 1		Day 15 ±2	Day 45 ±5	Day 105 ±10	
Informed Consent	X						
Inclusion/Exclusion ¹	X						
Demographics	X						
Montreal Cognitive Assessment (MOCA)	X						
Medical and Social History (Including Pre-Stroke Modified Rankin Scale (mRS))	X						
Medication Checklist	X	X					
Vital signs	X						
Fugl-Meyer Assessment– Upper Extremity Scale	X	X		X	X	X	
NIH Stroke Scale (NIHSS)		X					
Transcranial Magnetic Stimulation (TMS)		X ¹		X			
Randomization			X ²				
tDCS Treatment Activation Code Request (Retrieved at beginning of every Treatment Session)			X				
tDCS Questionnaires (Pre-Stimulation, Post-Stimulation, Post mCIMT)			X				
tDCS			X				
Modified Constraint Induced Movement Therapy (mCIMT)			X				
Wolf Motor Function Test (WMFT)		X		X	X	X	
Stroke Impact Scale (SIS)		X		X	X	X	
MRI		X ¹		X			
Concomitant Therapy				X	X	X	
Blindedness Assessment			X ⁴				
Visual Analog Scale			X ⁴				
End of Study							X

1. A urine pregnancy test for all women of child-bearing potential will be given at this visit.

2. Randomization ONLY occurs at 1st Treatment Session

3. This visit can be broken up over several days. All baseline activities need to take place prior to Day 1 treatment activities. Please see MOP and FAQs for more details on this visit.

4. End of Treatment ONLY occurs at Final Treatment Session

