2.3 RISK/BENEFIT ASSESSMENT

2.3.1 KNOWN POTENTIAL RISKS

- **General Risk Loss of Confidentiality:** It is expected that this risk will be low because of numerous safeguards that will be in place, including standard data management procedures at the NDMC.
- **tDCS:** Extensive animal and human evidence and theoretical knowledge indicate that tDCS protocols up to 2 mA are safe and tolerable⁷⁵⁻⁷⁷. Recently, a Phase I study evaluated the safety and tolerability of tDCS doses up to 4mA in patients with ischemic strokes; the study used a 3+3 study design and escalate dose to 4mA without meeting pre-specified safety rules. Overall, tDCS incurs no significant risk to human subjects per FDA determination. Commonly reported side effects in the literature are as follows: skin redness under the electrode, skin irritation with itching, tingling, burning sensation, and transient headache (which is mostly due to the tight elastic headband that holds the electrode in place). Any skin injury is a very rare side effect (1 out of 1000). Theoretical risks at high dose (e.g., 4mA) might involve second degree skin burns and clinical seizures, but these risks were not observed in the phase 1 safety study. Subjects will be carefully monitored for any potential safety or tolerability issues during each interventional session.

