7 STUDY INTERVENTION DISCONTINUATION AND SUBJECT DISCONTINUATION/WITHDRAWAL

7.1 DISCONTINUATION OF STUDY INTERVENTION

Discontinuation from tDCS and mCIMT intervention does not mean discontinuation from the study, and remaining study outcome assessments should be completed as indicated by the study protocol. If a clinically significant finding is identified (including, but not limited to changes from baseline) after enrollment, the investigator or qualified designee will determine if any change in subject management is needed. Any new clinically relevant finding will be reported as an adverse event (AE). An investigator may discontinue or withdraw a subject from study intervention for the following reasons:

- Pregnancy, but it is unlikely as woman of child-bearing potential will have urine pregnancy test to confirm or exclude the possibility of a pregnancy.
- Significant study intervention non-compliance, defined as missing >2 sessions out of 10 sessions and unable to make it up within the 2 week/14 days intervention period;
- If any adverse event (AE), laboratory abnormality, other medical condition or situation occurs such that continued participation in the study intervention would not be in the best interest of the subject.
- Disease progression (e.g., 4 points or more increases in the NIHSS score or recurrent stroke) which requires discontinuation of the study intervention.
- If a subject meets an exclusion criterion (either newly developed or not previously recognized) that precludes further study participation.
- Subject suffers another stroke, neurological or neuromuscular disease during the study period that may have an impact on motor recovery.

The reason for intervention discontinuation from the study will be recorded on the Case Report Form (CRF). The subject should continue to be followed and have all study assessments.

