10.1.1.2 CONSENT PROCEDURES AND DOCUMENTATION

Informed consent is a process that is initiated prior to the individual's agreement to participate in the study and continues throughout the individual's study participation. Consent forms will be Institutional Review Board (IRB)-approved, and the subject will be asked to read and review the document. The investigator will explain the research study to the subject/LAR and answer any questions that may arise. A verbal explanation will be provided in terms suited to the subject's comprehension of the purposes, procedures, and potential risks of the study and their rights as research subjects. Subject/LAR will have the opportunity to carefully review the written consent form and ask questions before signing. Subject/LAR should have the opportunity to discuss the study with their family or surrogates or think about it prior to agreeing to participate. Subject/LAR will sign the informed consent document prior to any procedures being done specifically for the study. Subject who is cognitively capable will sign informed consent; If subject is unable to provide written informed consent due to cognitive impairment (e.g., NIH Stroke Scale Level of Cognition Questions 1-3 combined score ≥ 3), a Legally Authorized Representative (LAR) will sign informed consent instead. During the follow-up visit, subject who was initially cognitively impaired

will be reassessed his/her cognition by study team member, if subject regains cognitive capability, he/she will be given an opportunity to decide if he/she still wants to remain in the study. Subject/LAR must be informed that participation is voluntary and that they may withdraw from the study at any time, without prejudice. A copy of the informed consent document will be given to the subject/LAR for their records. The informed consent process will be conducted and documented in the source document (including the date), and the form signed before the subject undergoes any study-specific procedures. The rights and welfare of the subjects will be protected by emphasizing to them that the quality of their medical care will not be adversely affected if they decline to participate in this study.

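### Neurological deterioration is defined by a rise in NIHSS, but the protocol schedules NIHSS only at Baseline 2 and does not explicitly require a later score

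*Combined protocol and SAP*

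**What the plan says.** Section 9.4.4 (Safety Analyses) names four clinically important adverse events: severe headache, second-degree skin burn, clinical seizure and neurological deterioration. The last is defined as at least a "4-point increase in NIHSS". Each is to be reported by arm with "two-sided 95% CIs and unadjusted relative risks", and Fisher's "exact tests will be used to assess intervention group differences in the rates of clinically important adverse events".

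Section 7.1 uses the same threshold as an example of disease progression that can end treatment: "4 points or more increases in the NIHSS score or recurrent stroke". It names no visit, trigger or timing for the repeat score.

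The Schedule of Activities (Section 1.3) has one NIHSS mark, at Baseline 2 (Day -6 to 1). None appears at the treatment sessions or at Days 15, 45 or 105.

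The only other use of the scale is in Section 10.1.1.2, where the "NIH Stroke Scale Level of Cognition Questions 1-3 combined score" helps decide whether a representative must consent. Follow-up there is a reassessment of cognition in subjects who were impaired at entry, not a repeat total score.

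**The concern.** Headache, burns and seizures can be recorded as they happen. Neurological deterioration as defined here is a change from baseline and needs two scores. Under the schedule as written, the second exists only if site staff decide to repeat the scale. Ascertainment then depends on local habit across about 15 sites, and the protocol does not say whether deterioration reported without a score counts as an event.

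Confirming safety is a secondary objective, and 4 mA is a candidate dose for Phase III. Section 9.4.4 notes that none of these events occurred in the Phase I study, so zero events is a plausible result here too. How much reassurance that gives depends on how completely the event was looked for. A score not taken cannot be recovered later.

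**Working it through.** **Tracing the scale.** NIHSS appears in four places in the protocol:

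| Place | Use | Requires a post-baseline total score? |
|---|---|---|
| Section 1.3 | Baseline 2 assessment | No |
| Section 7.1 | Example reason to stop treatment | Implied, not stated |
| Section 9.4.4 | Definition of the safety event | Presupposed, not stated |
| Section 10.1.1.2 | Capacity to consent | No |

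In the same schedule FM-UE is marked at both baselines and all three follow-up visits, so the empty NIHSS cells do not look like a damaged table.

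**What other routes would catch.** During treatment there is monitoring at each of 10 sessions (Section 2.3.1) and recording of all AEs (Sections 2.3.3 and 8.2). FM-UE and WMFT follow at Days 15, 45 and 105. SAE reporting includes hospitalisation and persistent disability (Section 8.2.2). Two kinds of event can still be missed: a rise that nobody recognises as an AE, and a non-serious event judged unrelated after treatment ends, which Section 8.2 does not collect.

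**Size.** The plan gives no rate, sample size or power for this event, so there is no stated figure to reproduce. The inputs are:

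- n = 43 per arm (Section 9.2).
- s = the fraction of true events scored or reported, equal in all arms, with no false positives. Assumed range 75% to 100%.
- p = the true event rate in an arm.

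The probability of observing no events in an arm is (1 − s·p)^43.

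*Upper bound after zero events.* Setting this to 0.025 (exact two-sided 95%) gives p = [1 − 0.025^(1/43)]/s = 0.0822/s.

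*Chance of seeing at least one event.* With an assumed p = 5%, this is 1 − (1 − 0.05·s)^43.

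| s | Upper bound on true rate, 0 of 43 observed | Chance of at least one observed event if p = 5% |
|---|---|---|
| 100% | 0.0822/1.00 = 8.2% | 1 − 0.95^43 = 89% |
| 90% | 0.0822/0.90 = 9.1% | 1 − 0.955^43 = 86% |
| 75% | 0.0822/0.75 = 11.0% | 1 − 0.9625^43 = 81% |

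The interval the plan would report is the first row, whatever s is.

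*Comparison between arms.* With equal s, the ratio of expected proportions is (s·p1)/(s·p2) = p1/p2, so it is unchanged. What suffers is the count. For two arms of 43 with no events on sham, two-sided Fisher p is 0.026 with 6 events on active treatment and 0.055 with 5. At a conventional 5% level (Section 9.4.4 sets none), one missed event can change the result of such a comparison.

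**The case against.** The strongest reply is that this is an adverse event, not a scheduled endpoint. Section 9.4.4 summarises it by AE code alongside three other event-driven items, none of which has its own scheduled test. On that reading the 4-point threshold grades a deterioration once someone has noticed it, and the Baseline 2 score supplies the reference. The stopping reason in Section 7.1 works only if staff score for cause. Subjects are also seen often: "Subjects will be carefully monitored for any potential safety or tolerability issues during each interventional session", each session includes about two hours of therapist-led mCIMT, Section 7.1 requires new clinically relevant findings to be reported as AEs, and Day 15 brings FM-UE, WMFT, SIS, TMS and MRI.

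Much of this stands. For-cause scoring is implied, overt deterioration would usually be found, and not collecting non-serious unrelated events after treatment is a stated choice about the AE window. The assumed range for s has no source in the documents, and no trial decision is shown to turn on it. The Manual of Procedures, the AE form and the separate SAP may also contain the missing instruction.

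The gap in the text remains. Section 7.1 gives no trigger, timing or rule for a missing score. The session tool in Section 8.2 is a questionnaire on common tDCS effects and tolerability. FM-UE and WMFT measure the upper limb and cannot yield a change in NIHSS. If another study document already requires the repeat score, bringing the protocol into line is simple.

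**Conclusion.** The concern holds, at modest weight. A pre-specified safety comparison rests on a change from baseline for which the protocol provides only the baseline. The expected consequence is under-detection of this one item, with per-arm proportions and confidence limits too low by the share of events missed. At an assumed 75% to 100% capture, zero events in 43 is compatible with a true rate of up to 11.0% to 8.2%, whereas the reported limit would be 8.2% throughout.

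No bias in the expected relative risk is claimed. That rests on capture being equal across arms, which blinding makes reasonable but does not guarantee. The true share missed is unknown, and the conclusion is limited to the protocol text. The change should be made, but the primary efficacy analysis does not depend on it.

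**What to change.** - Add NIHSS to the Schedule of Activities at Follow-Up 1 (Day 15).
- State that a for-cause NIHSS is required whenever deterioration is suspected, during treatment or follow-up.
- Count an event from either score, or from deterioration reported as an AE or SAE when no score exists.
- Keep all randomised subjects as the denominator, in line with Section 9.3, and report how many in each arm had a post-baseline NIHSS.

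The cost is a few minutes at an existing visit, one CRF page and a protocol amendment, with no extra visit. A single Day 15 score will still miss transient or later events that are not scored for cause, so the for-cause rule is needed as well.
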